6.1.5 Pregnancy

In the unlikely event that a subject becomes pregnant from the time point of signing the Informed Consent until the end of the study, study procedures that are contraindicated during pregnancy and/or lactation (e.g. x-rays) will not be obtained. However, the subject will continue to be followed and information will be collected regarding the outcome of the birth.

6.1.6 Study Site Discontinuation

Study site participation may be discontinued if the Sponsor, the Investigator or the approving Ethics Committee of the study site determines it necessary for medical, safety, regulatory or other reasons consistent with applicable laws, regulations and GCP.

6.1.7 Revisions

Subjects who have undergone a revision THA procedure to the primary SMF Short Modular Femoral stem, following the initial surgery, will be considered discontinued from the date of the revision procedure and will not receive any further study-related follow-up from this date. The End of Study CRF and Serious Device Adverse Event (SDAE) case report form will be completed to document the date of revision, adverse events and any radiographic assessment if available.

6.1.8 Study Discontinuation by Sponsor

The study will be discontinued if the Sponsor decides it necessary for medical, safety, regulatory or other reasons consistent with applicable laws, regulations and GCP. The Sponsor may also discontinue the study for no reason.

If the study has been discontinued for safety reasons, the Sponsor will advise the Investigator on the proper procedure to ensure the safety of enrolled subjects is maintained.

For each case, information will be documented on the Study Termination Form, detailing circumstances leading to the discontinuation.

7.0 Safety Reporting

An adverse event is any untoward medical occurrence, unintended disease or injury, or untoward clinical signs (including abnormal laboratory findings) in subjects, whether or not related to the investigational medical device. All adverse events and device deficiencies noted by study staff or reported by the subject occurring from the time of signing the informed consent through to study completion must be recorded on the appropriate CRFs and reported as below. This includes worsening of any conditions previously recorded as part of the medical history assessment.

Adverse Device Effects occurring after study completion will be handled as product complaints reportable by the Sponsor and will not be entered into the study database.

7.1 Definitions for Safety Reporting

7.1.1 Adverse Event (AE)

An AE is any untoward medical occurrence, unintended disease or injury, or untoward clinical signs (including abnormal laboratory findings) in subjects, users or other persons, whether or not related to the investigational medical device.

7.1.2 Adverse Device Effect (ADE)

An ADE is an adverse event related to the use of an investigational medical device.

This definition includes:

- adverse events resulting from insufficient or inadequate instructions for use, deployment, implantation, installation, or operation, or any malfunction of the investigational medical device
- any event resulting from use error or from intentional misuse of the investigational medical device

7.1.3 Serious Adverse Device Effect (SADE)

An SADE is an adverse device effect that has resulted in any of the consequences characteristic of a serious adverse event.

7.1.4 Serious Adverse Event (SAE)

An SAE is an adverse event that:

- led to death
- led to serious deterioration in the health of the subject, that either resulted in:
 - 1) a life-threatening illness or injury, or
 - 2) a permanent impairment of a body structure or a body function, or in-patient or prolonged hospitalization, or medical or surgical intervention to prevent life-threatening illness or injury or permanent impairment to a body structure or a body function
- led to fetal distress, fetal death or a congenital abnormality or birth defect

Planned hospitalization for a pre-existing condition, or a procedure required by the protocol, without serious deterioration in health, is not considered a serious adverse event.

7.1.5 Unanticipated Serious Adverse Device Effect (USADE)

A serious adverse device effect which, by its nature, incidence, severity or outcome has not been identified in the current version of the risk analysis report or the clinical investigation plan.

7.1.6 Device Deficiency

A device deficiency is an inadequacy of a medical device with respect to its identity, quality, durability, reliability, safety or performance. Device deficiencies include malfunctions, use errors, and inadequate labelling.

For the purpose of this study, device deficiencies should be reported when they concern any component of the study device.

7.1.7 Revisions

All events that lead to revisions will be collected as an SADE.

7.2 Safety: Investigator's Responsibilities

The Investigator shall record required safety events and observed device deficiencies, together with an assessment, in the subject's source data and the appropriate CRF and submit them to the Sponsor according to the timelines described below.

At each contact with the subject, the Investigator must seek information on AEs by specific questioning and, as appropriate, by assessment of the subject. These AEs must be recorded in Standard English medical terminology. AEs should be followed by the Investigator until the events are resolved, the subject is lost to follow-up or through to the end of the study, whichever timing occurs first. Unresolved AEs at the end of the subject's participation will be monitored by the Investigator as part of the site's normal standard of care.

The Investigator will categorize AEs as mild, moderate or severe based on the following definitions:

- **Mild:** the subject is aware of the sign or symptom, but finds it easily tolerated. The event is of little concern to the subject and/or little clinical significance. The event is not expected to have any effect on the subject's overall health or wellbeing.
- **Moderate:** the subject has discomfort enough to cause interference with or change in usual activities. The event is of some concern to the subject's health or wellbeing and may require medical intervention and/or close follow-up.
- **Severe:** the adverse event interferes considerably with the subject's usual activities. The event is of definite concern to the subject and/or poses substantial risk to the subject's health or wellbeing. The event is likely to require medical intervention and/or close follow-up and may be incapacitating or life threatening. Hospitalization and treatment may be required.

The Investigator is responsible for describing the relationship of the AE to the study device/procedure based on the following definitions:

- **Unrelated:** the event is clearly not related to the study device or procedure
- **Possible:** the event may or may not be related to the study device or procedure. A relationship cannot be ruled out
- **Definite:** the event is clearly related to the study device or procedure

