8.3.2 Analysis of Secondary Endpoints

- Revision of any component for any reason – Revision will be evaluated as the frequency of subjects with component revision at the end of study and expressed as a percentage of the full analysis set.
- Standard of Care Radiographic assessments
 - Loosening as indicated by radiolucencies > 2mm - a binary variable will be used to categorize subjects with radiolucencies > 2mm or below at all recorded time points. The frequencies together with percentages will be reported. The results will be further categorized as subjects with pain, swelling and functional limitations.
 - Evidence of surface wear or particulate debris generation as indicated by early osteolysis, implant migration, or other clinical or radiographic abnormalities such as pseudo tumors or corrosion

The presence of surface wear and all types radiographic abnormalities will be summarized as frequencies together with percentages at all recorded time points.

- HOOS JR Questionnaire
 - The score will be calculated to assess clinical efficacy

The HOOS score will be summarized using mean, median, SD, minimum and maximum at all recorded time points for all subjects. The results will be further categorized as subjects with pain, swelling and functional limitations. An exploratory t-test will be fitted to evaluate the difference between baseline and end of study scores.

- Device Related Adverse Events
 - Safety will be evaluated by assessing the frequency and nature of Device related adverse events as defined in the Safety Reporting section

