10.0 Risk – Benefit Analysis

10.1 Study Related Risks

Possible risks that may occur as a result of this study are:

- **X-Ray Exposure:** This study involves the use of x-ray evaluation. X-ray exposure is cumulative over a lifetime and total exposure should be kept to a minimum. However, if the x-ray exposure when participating in the study is equivalent to the exposure the subject would receive if they chose not to participate in the study, there is no additional risk associated with this study.
- **Loss of Confidentiality:** As a result of participating in the study there could be a risk of loss of protected subject information confidentiality. All applicable confidentiality standards and data protection and privacy laws will be followed by the Sponsor, Smith & Nephew, to ensure that data collection is handled in confidence. Data will be coded and handled only by appropriately qualified and authorized personnel.
- **Phlebotomy:** Blood draws will be required to obtain blood for metal ion assessment of cobalt chrome and chromium levels. Pain and bruising and possible infection at the site of blood draw and fainting may occur. The risk for these events will be reduced by use of approved medical equipment for blood draws and personnel trained in phlebotomy.
- **Metal artifact reduction sequence (MARS) magnetic resonance imaging (MRI)/Computerized tomography (CT):** MARS MRI will be indicated for study subjects who are symptomatic according to the Protocol. Radiologic evaluations used in this study are to be considered standard of care. There is no additional study-related radiologic exposure. The monitoring of symptomatic study subjects with MARS MRI or CT (where MRI is not recommended) will follow standard of care recommendations.

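### The single causality rating in section 7.2 merges device and procedure, so it cannot by itself supply the device-only adverse event counts that the plan calls for

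*Combined protocol and SAP*

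**What the plan says.** Section 7.2 sets the causality task: "The Investigator is responsible for describing the relationship of the AE to the study device/procedure based on the following definitions". Three levels follow: Unrelated, Possible and Definite. Each is worded for device or procedure jointly. Possible is "the event may or may not be related to the study device or procedure. A relationship cannot be ruled out"; Definite is "the event is clearly related to the study device or procedure". No other causality scale appears in the protocol.

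The definitions that feed the analysis refer to the device only. Section 7.1.2: "An ADE is an adverse event related to the use of an investigational medical device". Section 7.1.3 builds on it: "An SADE is an adverse device effect that has resulted in any of the consequences characteristic of a serious adverse event". Revisions have their own rule in 7.1.7: "All events that lead to revisions will be collected as an SADE".

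On analysis, 8.3.2 states: "Safety will be evaluated by assessing the frequency and nature of Device related adverse events as defined in the Safety Reporting section". Section 8.3.3 tabulates all adverse events as adverse device effects, serious adverse device effects, serious adverse events, unanticipated serious adverse device effects or device deficiencies. Section 10.1 foresees harm from study sampling: "Pain and bruising and possible infection at the site of blood draw and fainting may occur".

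**The concern.** The only causality instrument in the plan asks a different question from the one the endpoint needs. A Definite rating says that the device or a procedure caused the event, but not which. The 8.3.2 endpoint needs to know whether it was the device.

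This matters more here than in an implantation trial. Subjects join about 8 to 9 years after surgery and no implantation takes place in the study. The study procedures carried out on them are mainly blood draws and imaging. Section 7.0 requires every adverse event from consent onward to be recorded, so a faint or a bruise at sampling will enter the database. Symptomatic subjects are sampled annually and the others every three years, so any procedure events that slip into the device count would fall more heavily on the symptomatic group.

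The purpose of the study is safety data on a device taken off the market after a voluntary field safety corrective action. A device-related event count that could include needle-site events would be harder to interpret for that purpose.

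**Working it through.** The plan states no adverse device effect rate, power or calculated sample size on this point, so there is no figure to reproduce. The main check is a comparison of the text.

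**Step 1. What each place refers to.**

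| Place | Refers to |
|---|---|
| 7.2, all three levels | device or procedure, one answer |
| 7.1.2, adverse device effect | device only |
| 7.1.3, serious adverse device effect | device only, through 7.1.2 |
| 7.1.7, revisions | serious adverse device effect by rule, whatever the rating |
| 8.3.2, device-related events | device only, by reference to the Safety Reporting section |
| 8.3.3, tabulation | the defined categories, not the causality levels |

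**Step 2. Is there a link between them?** None is stated. No section says that Possible or Definite makes an event an adverse device effect. Section 8.3.2 refers to the Safety Reporting section for a definition of device-related, but that section does not define the term. The nearest items are the adverse device effect definition and the 7.2 scale, and they do not ask the same question.

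**Step 3. What does procedure mean?** It is not defined, and usage varies. Section 5.2 uses it for study procedures, 7.1.4 for procedures the protocol requires, Table 1 for the implant operation and 6.1.7 for revision surgery. On the first two readings a faint at a blood draw is rated Definite. On the last two it is Unrelated.

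**Step 4. Where would a minor blood-draw event go in 8.3.3?** The five categories have no row for an event that is neither serious nor device-related. Such an event is therefore either left out of the table or placed under adverse device effect. The plan does not say which.

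**Step 5. Size of one misclassified subject.** With n = 26 (section 8.0), 1/26 = 3.8%. Exact (Clopper-Pearson) 95% intervals:

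- 0/26 = 0% (0 to 13.2%)
- 1/26 = 3.8% (0.1 to 19.6%)
- 2/26 = 7.7% (0.9 to 25.1%)

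**Step 6. Could the number be estimated?** Only with an assumed event rate per draw, which the documents do not give. Follow-up from about year 8 or 9 to year 20 implies about 5 draws per subject on the three-yearly schedule and up to 13 on the annual one, baseline and end-of-study visits included. At full follow-up that is 26 × 5 = 130 to 26 × 13 = 338 draws. With d draws and an assumed rate p per draw, the expected number of subjects with at least one event is 26 × [1 − (1 − p)^d]:

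| Assumed p | d = 5 | d = 13 |
|---|---|---|
| 0.1% | 0.13 | 0.34 |
| 1% | 1.27 | 3.18 |
| 5% | 5.88 | 12.65 |

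The d = 13 column needs every subject to be symptomatic from baseline, with no death, loss or revision, so it is an outer bound. The range runs from negligible to large. These are also counts of blood-draw events, not of misclassified ones. They would inflate the device figure only if events were classed by the 7.2 scale and not by the 7.1.2 definition.

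**The case against.** A reader might infer that blood-draw events will be counted as device-related and that the adverse device effect figures will be wrong. The documents do not support that. A needle-site bruise does not meet the device-only definition in 7.1.2, whatever box is ticked under 7.2. Section 8.3.3 tabulates by the defined categories. Because procedure is undefined, nothing obliges the investigator to rate a blood-draw event Definite. No adverse device effect figures exist yet that could be wrong. All of this stands, and it limits the point to a risk of misclassification.

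A second objection is that the problem can be repaired later. The adverse event form is not among the documents and may already split the rating. Event descriptions and listings would usually reveal a bruise or faint at sampling, especially with so few subjects. Section 8.2 promises a more detailed SAP before database lock. This stands in part. A later SAP can set a counting rule, and obvious event terms can be reclassified. But that SAP may be finalised only after about twelve years of collection, and it cannot create a device-only rating that the investigator never gave. For events of uncertain cause, reclassifying from the description alone would be unreliable. If the form already has two ratings, 7.2 should say so.

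A third objection is that which causality levels count as related is a matter of convention that the SAP can settle. That is correct. Taken alone it is missing detail, and it is included in the fix only because the same sentence can settle it.

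**Conclusion.** The point holds as a mismatch between what is recorded and what is to be analysed. The stated rating covers device and procedure together, procedure is undefined, and the categories and endpoint that depend on causality concern the device. Procedure events may therefore be misclassified as device-related if the count is drawn from this scale.

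No frequency can be given. The only firm size is 3.8 percentage points per misclassified subject at the maximum enrolment of 26, and more if fewer enrol. The conclusion assumes that the adverse event form follows 7.2 as written. Revisions are unaffected, since 7.1.7 classifies them without using the scale. This is a cheap improvement to data collection and not a demonstrated error in the results.

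**What to change.** In 7.2 and on the adverse event form, replace the combined rating with two: relation to the SMF device, and relation to a study procedure. Define procedure, for example as blood sampling and imaging done under the protocol, and say where the original implant operation belongs.

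Add to 7.2 and 8.3.2 that adverse device effects, serious and unanticipated serious adverse device effects, and the device-related count use the device rating only, with the 7.1.7 rule for revisions kept as it is. State which levels count as related. One option is Possible plus Definite, with Definite alone shown alongside.

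The cost is one extra field on the form, slightly more data entry per event, and a few sentences of protocol text. The change is most useful early in follow-up, because ratings already given on the combined scale would have to be revisited event by event.

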7.3 Timelines for Submission of Safety Information

The timelines begin when the Investigator becomes aware of the event.

The Investigator will report to the Sponsor:

- As soon as possible, but **no greater than 24 hours upon becoming aware of the SAEs, SADEs, USADEs and device deficiencies that could have led to a SADE.**
- **Revisions: within 24 hours upon becoming aware of the event.** The Sponsor will provide an explant retrieval kit on becoming aware of a revision and ask the Investigator to return any revised components for retrieval analysis, if possible.

Upon request, the Investigator may also be asked to supply the Sponsor with any additional information related to the safety reporting of a particular event.

The Principal Investigator will be responsible for reporting SAEs, SADEs, USADEs, and device deficiencies that could have led to a SADE, as required by the IRB/EC.

7.4 Safety Reporting: Sponsor's Responsibilities

The Sponsor will provide progress reports on safety events to the Investigator to report to the Ethics Committee as required.

The Sponsor will also in case of SAEs and device deficiencies that could have led to SAEs, determine whether the risk analysis needs to be updated and assess whether corrective or preventive action is required.

8.0 Statistical Procedures

This is a single center, single arm, consecutive series study to evaluate the safety outcomes of hip arthroplasty with the SMF Short Modular Femoral Stem THA system. Up to 26 subjects will be enrolled in the study. The sample size was chosen based on the feasibility of recruitment only without regard for statistical power as this is a descriptive study and there is no available previous data for sample size justification.

8.1 Analysis Population

Intent-to-Treat (ITT) Population

The ITT population includes all subjects who met the inclusion criteria and are sequentially enrolled to the study based on medical record review and confirmation of Short Modular Femoral Stem implant surgery for a THA arthroplasty prior to IRB/EC approval of this protocol.

Per Protocol (PP) Population

The Per-protocol population (PP) population includes all enrolled subjects who received the assigned treatment and do not have major protocol violations. The PP population will be established after a review of protocol deviations. All efficacy analyses will be performed on the PP population.

8.2 Statistical Design

A Statistical Analysis Plan (SAP) will be written and finalized prior to database lock. The following is a brief description of the analyses to be described in this plan. The SAP will be more detailed and account for all analyses.

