Study Objective	The primary objective of this study is to provide safety data for the SMF Short Modular Femoral Stem Hip System up to a follow up period of 20 years post implantation
Primary Endpoint	Safety Data based on the following assessments: 
 ▪ Whole blood cobalt and chromium ion levels collected annually for symptomatic subjects and every 3 years for non-symptomatic subjects ▪ Metal artifact reduction sequence (MARS) magnetic resonance imaging (MRI) or Computed Tomography (CT) in subjects with whole blood cobalt and/or chromium > 7 parts per billion (ppb)
Secondary Endpoints	
 ▪ Standard of Care Radiographic assessments ▪ HOOS JR Hip Questionnaire ▪ Revision of any component of the study device for any reason ▪ Adverse events assessment
Length of Study	Approximately Twelve Years. Subjects have been implanted with the SMF Device in 2009 and 2010 at the investigational site. The Baseline visit will be determined as the first visit to site after Ethics approval for the study has been received. This will be approximately 8-9 years post implant. Enrolled subjects will be followed up to 20 years post SMF implant
Number of Sites	1 site (Australia)
Sample Size	Up to 26 subjects based on feasibility only
Inclusion Criteria	
 ▪ Subject has undergone primary total hip arthroplasty with the SMF Short modular femoral stem at the study site and still has the original implant at the time of Ethics Committee (EC) approval of the study ▪ Subject is willing and able to participate in follow-up visits at the study site

Exclusion Criteria	
 ▪ The Subject, in the opinion of the PI, has an emotional or neurological condition that would affect their ability or willingness to participate in the study including mental illness, mental retardation, drug or alcohol abuse ▪ Subject is known to be at risk for lost to follow-up or failure to return for scheduled visits
---------------------------	--

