3.0 Study Design

This is a single arm, consecutive series study to collect relevant clinical, laboratory and radiological data in up to 26 subjects, who have been implanted with the SMF Short Modular Femoral Stem THA system at 1 site in Australia.

The Baseline visit will be determined as the first visit to site after Ethics approval for the study has been received. This will be approximately 8-9 years post implant. Enrolled subjects will be followed up to 20 years post SMF implant. The Baseline visit assessments are described in Section 5.5 and 5.6. Post Baseline, the study will allow for metal ion assessments every 3 years for asymptomatic subjects and annual assessments for subjects with pain, swelling, and/or functional limitations if assessed by the Principal Investigator to be related to the SMF implant, having ruled out all other probable causes for the subject. If the subject has elevated whole blood cobalt or chromium (defined as >7ppb) a MARS MRI or CT will be obtained. These types of imaging techniques are aimed at

detecting inflammatory degenerative evolution of periarticular soft tissues including pseudo-tumors. A functional Questionnaire, HOOS JR Questionnaire will be completed at all patient site visits.

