8.2.1 General

The subjects will be described and summarised using the collected baseline demographic and medical variables which include but are not limited to age, gender, ethnicity, medical and medication history, diagnostic factors.

Primary and secondary endpoints will be evaluated using listings and appropriate summary statistics. The summary statistics for both primary and secondary outcomes will be reported together with a 95% confidence interval to assess the degree of precision in the estimates.

Summary statistics for baseline data, primary and secondary endpoints will be given according to the nature of the variable, continuous or categorical. For categorical variables, the number of observations, mean, standard deviation, median, minimum, and maximum will be presented, while for categorical variables the number of observations, frequency, and percentages will be reported.

All statistical tests will be exploratory in nature as the study is not powered for any statistical testing. Appropriate parametric and/or non-parametric analyses will be chosen for statistical analysis. Test of association for the table of counts will be based on the Fisher's Exact Test unless otherwise inappropriate. The exploratory analysis of continuous variables will be done using t-test if appropriate. The Wilcoxon rank-sum test will be explored if the data is non-normal. All statistical tests will be considered at 5% significance level.

All statistical analyses and calculation of confidence intervals will be performed using SAS software.

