12.0 Data Handling and Record Keeping Requirements

CRFs will be supplied by the Sponsor. Subjects will be identified by a Study ID number and subject identification code. Only the Investigator site will have the key to identify individual subjects. The Investigator will be responsible for the timely and accurate completion of CRFs. Data collected for the purposes of this protocol are to be recorded on the CRFs at the time of the scheduled visits. Completed CRFs should be sent to the Sponsor, either by fax or by e-mail, as soon as possible.

All documents related to the study must be securely archived at the study site or in an archiving facility.

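### The SAP may stay open until database lock, 11-12 years after unmasked data start to arrive, with the safety denominator unsettled and no periodic ion or imaging summary specified

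*Combined protocol and SAP*

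**What the plan says.** **Timing.** Section 8.2 (Statistical Design): "A Statistical Analysis Plan (SAP) will be written and finalized prior to database lock". No earlier milestone appears. The Protocol Synopsis gives the length of study as "Approximately Twelve Years. Subjects have been implanted with the SMF Device in 2009 and 2010 at the investigational site". Section 3.0 says of the Baseline visit: "This will be approximately 8-9 years post implant". The Synopsis adds: "Enrolled subjects will be followed up to 20 years post SMF implant".

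**Data flow.** Section 8.0 describes a single-centre, single-arm study of up to 26 subjects, and no masking is described anywhere. Section 12.0: "Completed CRFs should be sent to the Sponsor, either by fax or by e-mail, as soon as possible".

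**Populations.** Section 8.1 defines ITT and per-protocol (PP) sets and assigns all efficacy analyses to PP. PP excludes subjects with major violations, a term it does not define, and "The PP population will be established after a review of protocol deviations". Section 8.3, headed Efficacy Analysis, contains the primary endpoint, which 8.3.1 itself calls a safety assessment. Section 8.3.2 uses a full analysis set that 8.1 does not define. Section 8.3.3 (safety endpoints) names no population.

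**Methods.** Section 8.2.1: "Appropriate parametric and/or non-parametric analyses will be chosen for statistical analysis". It also promises listings, summary statistics and 95% confidence intervals, and calls all tests exploratory.

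**Review during the study.** Under Section 7.4 the sponsor supplies progress reports on safety events and will also "in case of SAEs and device deficiencies that could have led to SAEs, determine whether the risk analysis needs to be updated".

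**The concern.** Finalising a SAP before lock is ordinary practice, and it protects the analysis when those writing the plan cannot yet see the results. That protection is weak here. There is one unmasked arm, few subjects, and a sponsor that holds their results as they accrue.

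The choice that matters most is who is counted. Section 13.0 treats missed data collection and out-of-window visits as deviations, and over more than a decade some of these are foreseeable. Deciding late which of them are major can decide whose ion levels enter the summary. Section 1.0 says the device was removed from the market as a precaution over a possible greater risk of revision, so readers will want to know that the denominator was not chosen after the fact.

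A second gap makes the first worse. If no group-level table of ions or imaging is called for along the way, a gradual change across subjects may go unexamined as a group until the final report.

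**Working it through.** **1. The plan's own study length.** Inputs: Baseline at 8-9 years post implant (Section 3.0) and end of follow-up at 20 years (Synopsis).

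- 20 − 8 = 12 years; 20 − 9 = 11 years.

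The stated figure of about twelve years is reproduced. This is also the time from a subject's Baseline to the end of that subject's follow-up, and lock cannot come before the last subject finishes if the study runs to plan.

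**2. How much data could be held before the SAP must be final.** Inputs: at most 26 subjects; ion sampling at Baseline, every 3 years (annually if symptomatic) and at end of study (Section 3.1 and Table 1). Full retention is assumed.

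| Schedule | Visit years post implant | Draws per subject | Total for 26 |
|---|---|---|---|
| 3-yearly, Baseline at 8 | 8, 11, 14, 17, 20 | 5 | 130 |
| 3-yearly, Baseline at 9 | 9, 12, 15, 18, 20 | 5 | 130 |
| Annual, Baseline at 8 | 8 to 20 | 13 | 338 |
| Annual, Baseline at 9 | 9 to 20 | 12 | 312 |

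The annual rows are the extreme in which every subject is symptomatic throughout. In every row all results could be with the sponsor before the SAP falls due. That the CRFs carry the ion values is an inference: Section 5.5 lists ion assessment among the data collected, and Section 12.0 has study data recorded on CRFs.

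**3. What the choice of denominator can do.** The documents give no expected proportion above 7 ppb, so the counts here are assumptions: 3 subjects above the threshold and 3 PP exclusions. Intervals are exact (Clopper-Pearson): lower limit = Beta(0.025; x, n − x + 1), upper limit = Beta(0.975; x + 1, n − x), with lower limit 0 when x = 0.

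| Set analysed | x/n | Proportion | 95% CI |
|---|---|---|---|
| All enrolled | 3/26 | 11.5% | 2.4-30.2% |
| The three high subjects excluded | 0/23 | 0% | 0-14.8% |
| Three other subjects excluded | 3/23 | 13.0% | 2.8-33.6% |

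For 0/23 the upper limit is 1 − 0.025^(1/23) = 14.8%. The estimate runs from 0% to 13.0% depending only on which three subjects are left out. No hypothesis test is involved.

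**4. What reaches the sponsor's review during the study.**

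- Section 7.0 counts abnormal laboratory findings as adverse events, but no section says that a result above 7 ppb must be recorded as one.
- Section 7.3 sets 24-hour reporting for SAEs, SADEs, USADEs, device deficiencies that could have led to a SADE, and revisions. A non-serious laboratory event is not on that list.
- Section 7.4 ties the risk-analysis decision to SAEs and to device deficiencies that could have led to SAEs. Its progress reports cover safety events, have no stated schedule, and do not mention ion or MRI/CT data.

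A non-serious rise across the group can therefore be known subject by subject without any provision requiring it to be tabulated or put to the risk-analysis review.

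**The case against.** The other side has real substance.

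- **The study is descriptive.** Sections 8.0 and 8.4 say so, and 8.2.1 calls every test exploratory. A reader might infer that late choices inflate the false-positive rate in a way that matters. The documents do not support that, because there is no confirmatory alpha to protect. Section 8.2.1 also fixes the core summaries and ties the rank-sum test to non-normal data. This stands, and the point does not rest on error rates. It does not answer the denominator problem, which affects the descriptive estimates themselves.
- **Data are not withheld until the end.** A reader might infer that the primary safety data are assembled only at lock. Section 8.2 dates the SAP, not data assembly, and Section 12.0 sends CRFs to the sponsor throughout. What is missing is a specified aggregate summary.
- **Safety routes exist.** A reader might infer that rising ions could not reach the risk analysis without an SAE. That is too strong. Qualifying device deficiencies also trigger review, abnormal laboratory findings can be adverse events, progress reports are required, and Section 1.0 describes continual product monitoring. The supportable statement is that such a rise need not reach the review.
- **A latest date is not a planned date.** The SAP could be written early, and nothing shows that its author will know every value. That is fair; the weakness is that the protocol permits it.
- **The population is assigned.** Read literally, Sections 8.1 and 8.3 put the primary endpoint in PP. Even so, PP membership remains open, and using PP for an endpoint the plan calls safety conflicts with that label.

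**Conclusion.** The concern holds, at moderate weight. The protocol permits the SAP to be finalised 11-12 years after unmasked results on at most 26 subjects begin to arrive, while PP membership and the primary-endpoint population remain unsettled. Under the assumed counts, that freedom moves the proportion above 7 ppb between 0% and 13.0%, against 11.5% in all enrolled subjects. Separately, no periodic aggregate summary of ion or imaging data is specified, and the risk-analysis trigger does not cover non-serious findings.

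Finalising before lock would not be a fault in itself. The weakness lies in combining it with open data and open populations. The size rests on three subjects above threshold and three exclusions, neither of which is in the documents, and on the inference that CRFs carry ion results. Nothing here shows that the sponsor intends to choose with results in view.

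**What to change.** 1. **Section 8.2.** Require the SAP to be finalised and dated before the sponsor receives any post-baseline ion or imaging result. If some have already been received, finalise it now and state which data had been seen. Log later changes with date and reason. The trigger should be receipt of data, since individual results are informative before anyone summarises them. At most the Baseline round would then be known beforehand.
2. **Section 8.1.** State that the primary safety endpoint is analysed in all enrolled subjects, with PP as a sensitivity analysis. List the criteria for PP exclusion and have them applied without reference to ion or imaging values. Bring the populations named in 8.3 to 8.3.3 into line, including the undefined full analysis set.
3. **Section 7.4.** Add a descriptive table of cobalt, chromium and MRI/CT findings after Baseline and after each 3-year round, to go into the progress report and the risk-analysis review.

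The cost is earlier SAP drafting and about five short tables (Baseline, three further rounds and end of study, as in the 3-yearly rows above). No test is added, and sample size, alpha and clinical management are unchanged.
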